Appendix 11: Examples of Low-Fat and High-Fat, High-Calorie Meals

Low-fat breakfast:

A) 2 slices of white bread toast, 1 tablespoon light fat margarine, 1 tablespoon of jelly, and 8 ounces of skim milk (319 calories and 8.2 grams of fat)

B) 1 cup of cereal, 1 slice of toast with jam, 8 ounces of skim milk, and 1 cup of decaffeinated coffee or tea (520 calories and 2 grams of fat)

A high-fat breakfast consists of the following and may be adapted to the local regional preference: 2 eggs fried in butter, 2 strips of bacon, 2 slices of white bread with butter, 1 croissant with 1 slice of cheese, and 8 ounces of whole milk. This representative high-fat breakfast contains approximately 1000 calories and 58 grams of fat.

Appendix 12: National Cancer Institute Common Terminology Criteria for Adverse Events

The NCI CTCAE, version 5.0 can be accessed at the following location: http://evs.nci.nih.gov/ftp1/CTCAE/CTCAE_4.03_2010-06-14_QuickReference_8.5x11.pdf

RECIST v1.1

Tumor lesions are to be categorized as measurable *versus* non-measurable and target *versus* non-target based on RECIST v1.1 ([Eisenhauer et al, 2009](#)).

Measurable Lesions

Tumor lesions: Must be accurately measured in at least 1 dimension (longest diameter in the plane of measurement is to be recorded) with a minimum size of:

- 10 mm by CT scan (CT scan slice thickness no greater than 5 mm)
- 10 mm calliper measurement by clinical exam (lesions which cannot be accurately measured with callipers should be recorded as non-measurable)
- 20 mm by chest X-ray

Malignant lymph nodes: To be considered pathologically enlarged and measurable, a lymph node must be ≥ 15 mm on the short axis when assessed by CT scan.

Non-measurable Lesions

All other lesions, including small lesions (longest diameter < 10 mm or pathological lymph nodes with ≥ 10 to < 15 mm short axis) as well as truly non-measurable lesions, including leptomeningeal disease, ascites, pleural or pericardial effusion, inflammatory breast disease, lymphangitic involvement of skin or lung, abdominal masses/abdominal organomegaly identified by physical exam that is not measurable by reproducible imaging techniques.

Target Lesions

When more than 1 measurable lesion is present at baseline all lesions up to a maximum of 5 total (and a maximum of 2 lesions per organ) representative of all involved organs should be identified as target lesions and measured at baseline.

Target lesions should be selected on the basis of their size (lesions with the longest diameter), be representative of all involved organs, but in addition should be those that lend themselves to reproducible repeated measurements.

Pathological lymph nodes that are defined as measurable and identified as target lesions must have a short axis of ≥ 15 mm by CT scan. Only the short axis of these nodes contributes to the baseline sum.

A sum of the diameters (longest for non-nodal lesions, short axis for nodal lesions) for all target lesions will be calculated and reported as the baseline sum diameters. The baseline sum diameters will be used as reference to further characterize any objective tumor regression in the measurable dimension of the disease.

Non-target Lesions

All other lesions (or sites of disease) including pathological lymph nodes should be identified as non-target lesions and should also be recorded at baseline. Measurements are not required, and these lesions should be followed as 'present', 'absent' or 'unequivocal progression.'

The following criteria outlined in Table 6 and Table 7 will be used to assess response to treatment.

Table 6: Disease Response Criteria for Target and Non-target Lesions

Category	Response Criteria	
	Target Lesions	Non-target Lesions/Tumor Markers
Complete response (CR)	Disappearance of all target lesions. Any pathological lymph nodes (whether target or non-target) must have reduction in short axis to < 10 mm	Disappearance of all non-target lesions, and normalization of tumor marker level All lymph nodes must be non-pathological in size (< 10 mm short axis).
Partial response (PR)	A $\geq 30\%$ decrease in the sum of the diameter of target lesions, taking as reference the baseline sum diameter	Not applicable
Stable disease (SD) / incomplete response	Neither sufficient shrinkage to qualify for PR nor sufficient increase to qualify for progressive disease, taking as reference the smallest sum diameter since the treatment started	Persistence of 1 or more non-target lesion(s) and/or Maintenance of tumor marker levels above the normal limits
Progressive disease	A $\geq 20\%$ increase in the sum of the diameter of target lesions, taking as reference the smallest sum diameter recorded since the treatment started. In addition to the relative increase of 20%, the sum must also demonstrate an absolute increase of at least 5 mm, or The appearance of 1 or more new lesions	Appearance of 1 or more new lesions, and/or Unequivocal progression of existing non-target lesions

Table 7: Overall Disease Response Criteria

Target Lesions	Non-target Lesions	New Lesions	Overall Response
CR	CR	No	CR
CR	Incomplete response/SD	No	PR
PR	Incomplete response/Non-Progressive disease	No	PR
SD	Incomplete response/Non-Progressive disease	No	SD
Progressive disease	Any	Yes or no	Progressive disease
Any	Progressive disease	Yes or no	Progressive disease
Any	Any	Yes	Progressive disease

Abbreviations CR = complete response; PR = partial response; SD = stable disease.

Appendix 13: Local modification of the clinical study protocol (GBR)

FINAL VERSION DATE:	20 December 2023
COUNTRY CONCERNED:	United Kingdom
CENTRES CONCERNED:	All centres in United Kingdom
NATURE OF MODIFICATIONS	

- Update of inclusion criteria 4 and Appendix 7 to clarify acceptable contraception methods.- In line with CTFG guidance, an additional pregnancy test to be performed at the end of the relevant systemic exposure; at the 100-day safety follow up visit.- Clarification added to section 8.4 that all SAEs must be reported to the sponsor immediately and within 24 hours of awareness at the latest.	

Paragraph impacted 5.1 Inclusion Criterion- 4 - Sex and Contraceptive/Barrier requirements
Amended text:

Women of childbearing potential (WOCBP) must agree to abstain from sexual intercourse or to use 2 forms of contraception, one of which must be highly effective and one a barrier method (Appendix 7) highly effective (Appendix 7) forms of contraception, at least one of which must be a barrier method, from the time of giving informed consent throughout the study, and for 5 months after the last dose of study treatment.

Paragraph impacted Appendix 7 - Contraception considerations
Amended text:

Definition of acceptable contraception methods for the study: ~~Acceptable contraception methods for the study are those considered as highly effective methods~~, In addition to a highly effective method, the second form of contraception may include male or female condom with or without spermicide, cap, diaphragm or sponge with spermicide.

Paragraph impacted 4.1.2 Investigational Schedule

Amended text: a new cross (X) is present in the Table (4.1.2) 1 column safety follow-up 100 (+5) Days After Last Nivolumab Dose and line pregnancy test.

Table (19) 1 - Schedule of Assessments for Subjects in the Safety Lead-in Phase and Expansion Phase

Visit/Cycle	Screening ¹	Cycle 1 (21 Days)			Cycle 2 (21 Days)		Cycles 3 and 4 (21 Days)	Cycle 5 and Beyond (28 Days Each Cycle)	End of Treatment ²	Safety Follow-up ²		PFS Follow-up ³	Survival Follow-up
Study Day	D-28 to D-1	D1	D8	D15 (± 2 Days)	D1 (± 2 Days)	D15 (± 2 Days)	D1 (± 2 Days)	D1 (± 2 Days)	Within 7 Days After Last Dose	30 (+5) Days After Last Dose	100 (+5) Days After Last Nivolumab Dose		Every 12 weeks (± 2 weeks)
Allocation to IMP ⁴		X			X		X	X					
Informed Consent	X												
Inclusion/Exclusion Criteria	X												
Demographics	X												
Disease History	X												
Medical and Surgical History	X												
Complete Physical Exam	X												
Limited Physical Exam		X		X	X	X	X	X	X				
Height and Weight ⁵	X	X			X		X	X					
ECOG Performance Status	X	X			X		X	X	X	X			
Vital Signs ⁶	X	X		X	X	X	X	X	X				
12-lead ECG ^{7,8}	X	X	X	X	X		X	X	X	X			
LVEF (ECHO, MUGA scan, or	X												

Visit/Cycle	Screening ¹	Cycle 1 (21 Days)			Cycle 2 (21 Days)		Cycles 3 and 4 (21 Days)	Cycle 5 and Beyond (28 Days Each Cycle)	End of Treatment ²	Safety Follow-up ²		PFS Follow-up ³	Survival Follow-up
Study Day	D-28 to D-1	D1	D8	D15 (± 2 Days)	D1 (± 2 Days)	D15 (± 2 Days)	D1 (± 2 Days)	D1 (± 2 Days)	Within 7 Days After Last Dose	30 (+5) Days After Last Dose	100 (+5) Days After Last Nivolumab Dose		Every 12 weeks (± 2 weeks)
by other method according to institutional practice)													
Hematology ⁹	X	X		X	X	X	X	X	X				
Serum Chemistry ¹⁰	X	X		X	X	X	X	X	X				
Coagulation Studies ¹¹	X												
Pregnancy Test ¹²	X ¹²	X ¹²			X ¹²		X ¹²	X ¹²	X ¹²		X		
Thyroid Function Tests ¹³	X	X					X (only at C3D1)	X (every other cycle)	X				
Radiographic Evaluation of Disease ¹⁴	X (D-21)						X (only C3D1) ¹⁵	X ¹⁵ (every other cycle)	X ^{15,16}			X	
Ivosidenib Administration ¹⁷			X										
Nivolumab Administration ¹⁸		X			X		X	X (every cycle)					
Ipilimumab Administration ¹⁹		X			X		X						
IMP Compliance ²⁰					X		X	X	X				
Tumor Biopsy ²¹	X						X (± 7 days for biopsy collection)		X				

Visit/Cycle	Screening ¹	Cycle 1 (21 Days)			Cycle 2 (21 Days)		Cycles 3 and 4 (21 Days)	Cycle 5 and Beyond (28 Days Each Cycle)	End of Treatment ²	Safety Follow-up ²		PFS Follow-up ³	Survival Follow-up
Study Day	D-28 to D-1	D1	D8	D15 (± 2 Days)	D1 (± 2 Days)	D15 (± 2 Days)	D1 (± 2 Days)	D1 (± 2 Days)	Within 7 Days After Last Dose	30 (+5) Days After Last Dose	100 (+5) Days After Last Nivolumab Dose		Every 12 weeks (± 2 weeks)
Buccal Swab for Germ-line Mutation Analyses ²²	X												
Blood Sampling for Exploratory Biomarkers ²³	X				X		X	X	X				
Adverse Events ²⁴	X	X		X	X	X	X	X	X	X	X		
Prior and Concomitant Medications/Procedures ²⁵	X	X		X	X	X	X	X	X	X	X		
Subsequent Anti-cancer Therapy									X	X	X	X	X
Survival Status ²⁶													X

Abbreviations AE = adverse event; C = Cycle; CFR = Code of Federal Regulations; CT = computed tomography; D = Day; ECG = electrocardiogram; ECHO = echocardiography; ECOG = Eastern Cooperative Oncology Group; eCRF = electronic case report form; EOT = End of Treatment; FFPE = formalin-fixed paraffin-embedded; GDPR = General Data Protection Regulation; HIPAA = Health Insurance Portability and Accountability Act; ICF = informed consent form; IDH1 = Isocitrate dehydrogenase-1; IMP = investigational medicinal product; IV = intravenous; LVEF = left ventricular ejection fraction; MRI = magnetic resonance imaging; MUGA = multiple gated acquisition; PFS = progression-free survival; Q3W = once every 3 weeks; Q4W = once every 4 weeks; QTcF = heart rate-corrected QT interval by Fridericia's method; RTSM = Randomisation and Trial Supply Management; SAE = serious adverse event.

Note One, or two if required by local regulation, original information and consent form(s) must be completed, dated, and signed personally by the participant and by the person responsible for collecting the informed consent. According to each study participant's own preference, the ICF could be made available both printed on paper or/and electronically through a HIPAA, 21 CFR Part 11, and GDPR compliant web-based platform. Local regulations permitting, the electronic signature for the ICF could be made available to interested study participants. Interested study participants will be offered the possibility to replace certain in-person visits to the research site by televisits. This means that some study visits could be conducted using a HIPAA, 21 CFR Part 11, and GDPR compliant web-based platform, as per each study participant's own preference. Follow-up (for survival status until the end of the study) can be done remotely by using various telecommunication technologies including but not limited to phone, web-based remote video-calling, and shared electronic medical records.

1. Day -28 is relative to first dose of IMP.
2. All subjects will undergo an EOT assessment within 7 days after the last dose of IMP (for combination, this is to occur after all 3 IMPs have been discontinued). However, when this is not possible (e.g., dose delay more than 7 days), EOT assessment can be performed at the 30-day safety follow-up visit. A second Safety Follow-up will occur 100 (+5) days after last nivolumab dose or ipilimumab if no other anti-cancer therapy is initiated.
3. Subjects who discontinue study treatment for reasons other than disease progression or withdrawal of consent and are alive by EOT will enter PFS follow-up with the same schedule of assessments as before study treatment discontinuation, until documented disease progression, death, start of subsequent anti-cancer therapy, withdrawal of consent, or the end of study/study termination.
4. Allocation of IMP will occur via RTSM.
5. Height is to be obtained only at Screening assessment.
6. Systolic and diastolic blood pressure, heart rate, respiratory rate, and temperature. Assessments should be conducted while the subject is seated or supine.
7. Subjects with a QTcF of \geq 450 msec at baseline will not be allowed to enroll in the study. Up to three 12 lead ECG tests under stable condition can be performed at each visit during screening and throughout treatment and study follow-up.
8. ECG can be performed at any time during the study visit (on-site or at local clinic); however, it is required once weekly for the first 3 weeks of treatment, and then once every cycle for the duration of therapy.
9. Hematocrit, hemoglobin, red blood cell count, white blood cell count with differential, and platelet count. Hemoglobin criteria of \geq 9.0 g/dL or \geq 5.6 mmol/L at Screening must be met without packed red blood cell transfusion within the prior 2 weeks. Subjects can be on stable dose of erythropoietin (\geq approximately 3 months). On C1D1, assessments should be conducted prior to IMP administration.
10. Sodium, potassium, chloride, calcium, magnesium, phosphorus, carbon dioxide, albumin, glucose, blood urea nitrogen (BUN)/UREA, creatinine, alkaline phosphatase, alanine aminotransferase, aspartate aminotransferase, gamma glutamyl transferase, total bilirubin, direct bilirubin, and indirect bilirubin. On C1D1, assessments should be conducted prior to IMP administration.
11. Activated partial thromboplastin time and either prothrombin time or international normalized ratio.
12. For women of childbearing potential, a serum pregnancy test will be performed at Screening, and a urine pregnancy test will be conducted on the day of IMP administration and is to be confirmed negative prior to dosing. If the urine pregnancy test is positive and cannot be confirmed negative, a serum pregnancy test must be performed and shown to be negative within 24 hours prior to the first day of IMP administration. An extension up to 72 hours prior to the start of study treatment is permissible in situations where the results cannot be obtained within the standard 24-hour window.
13. Thyroid function test includes triiodothyronine (T3) or free T3, free thyroxine, and thyroid stimulating hormone. Thyroid function tests are to be performed every 6 weeks for the first 4 cycles and then every 8 weeks starting from Cycle 5 and to be performed at EOT. On C1D1, assessments should be conducted prior to IMP administration. Thyroid function test results obtained after the visit are acceptable so long as the value at screening was normal or considered not clinically significant per investigator assessment.
14. Tumor assessments will include all known or suspected disease sites. CT imaging of the chest, abdomen, and pelvis (torso) with triphasic IV contrast should be performed at baseline and on study. For subjects with allergy to IV iodine contrast, CT chest without IV contrast and MRI abdomen with IV contrast should be performed at baseline and on study. Brain scans with CT or MRI should be performed at baseline in subjects with known treated brain metastases and on study at the same imaging time points as torso imaging. Additional anatomy should be imaged based on the signs and symptoms of individual subjects at baseline and follow-up. Radiographic assessment (CT or MRI or other imaging modalities as appropriate per RECIST v1.1 Appendix 4) for evaluation of disease response to be conducted at Screening (Day -21 to Day -1), every 6 weeks (\pm 7 days) for the first 2 assessments (*i.e.*, through Week 12), and then every 8 weeks (\pm 7 days) thereafter independent of dose delays and/or dose interruptions, and/or at any time when progression of disease is suspected. Tumor assessment frequency can be reduced to every 12 weeks after 2 years of treatment initiation.
15. Response to treatment is to be assessed at this visit if the subject discontinues treatment for reasons other than disease progression or start of another anticancer therapy.
16. If a subject goes off treatment for reasons other than disease progression or withdrawal of consent from treatment, response assessments will be conducted at the EOT visit.
17. Ivosidenib is to be taken daily. Subjects should be instructed to take their daily dose at approximately the same time each day. Each daily dose should be taken with or without food. Subjects taking ivosidenib with food should be advised to avoid grapefruit or grapefruit products and avoid consuming a high-fat meal. If the subject forgets to take the daily dose, then they should take ivosidenib within 12 hours after the missed dose. If more than 12 hours have elapsed, then that dose should be omitted, and the subject should resume treatment with the next scheduled dose. The dose on C1D1, C1D15, and Day 1 of each cycle thereafter is to occur in-clinic to allow for pre-treatment assessments and to accommodate PK sampling. In subjects receiving the combination, on days when nivolumab and ipilimumab are administered, ivosidenib should be administered approximately 30 minutes before the start of the nivolumab infusion.
18. Nivolumab is to be administered over an approximately 30-minute IV infusion. Sites should make every effort to target infusion timing to be as close to 30 minutes as possible. However, given the variability of infusion pumps from site to site, a window between -5 minutes and +10 minutes is permitted (*i.e.*, infusion time is 30 minutes (-5 minutes/+10 minutes). When study treatments nivolumab and ipilimumab are to be administered on the same day, nivolumab is to be administered first. Nivolumab infusion must be promptly followed by a flush of diluent to clear the line of nivolumab before starting the ipilimumab infusion. The second infusion will always be the ipilimumab study treatment and will start after the infusion line has been flushed, filters changed, and subject has been observed to ensure that no infusion reaction has occurred.
19. Ipilimumab is to be administered over an approximately 30-minute IV infusion. Sites should make every effort to target infusion timing to be as close to 30 minutes as possible. However, given the variability of infusion pumps from site to site, a window between -5 minutes and +10 minutes is permitted (*i.e.*, infusion time is 30 minutes (-5 minutes/+10 minutes). When study treatments nivolumab and ipilimumab are to be administered on the same day, nivolumab is to be administered first. Nivolumab infusion must be promptly followed by a flush of diluent to clear the line of nivolumab before starting the ipilimumab infusion. The second infusion will always be the ipilimumab study treatment and will start after the infusion line has been flushed, filters changed, and subject has been observed to ensure that no infusion reaction has occurred. The time in between nivolumab and ipilimumab infusions is expected to be within approximately 30-minutes.
20. Treatment compliance for ivosidenib is to be assessed based on the drug diary and/or return of unused drug.
21. Tumor tissue for retrospective central laboratory confirmation of IDH1 gene mutation status and exploratory biomarker analysis at Screening is requested. Subjects will have locally documented presence of the IDH1 gene mutation for inclusion. If a subject cannot undergo a biopsy at Screening, collection of archival tumor tissue from the most recent biopsy/resection of at least 20 freshly cut, unstained FFPE slides (4-

5 µm each) plus 1 H&E slide will be submitted at a later time together with the pathology report upon sponsor's request. Tumor biopsies are to be collected at baseline, C3D1, and EOT from similar anatomical locations for exploratory biomarker analyses including PK/PD. In case of limited tissue amounts, biopsy samples will be formalin fixed and paraffin embedded. Please refer to the laboratory manual for priorities in tissue processing. If a required tumor biopsy (any time point) cannot be performed due to concerns around subject safety, a discussion with the Sponsor is required and biopsy can be omitted. Further details on screening and on-treatment biopsy collections are provided in the laboratory manual.

- 22. A buccal swab for germ-line mutation analysis will be obtained at Screening.
- 23. Blood samples for exploratory biomarker assessments, including plasma circulating tumor DNA, will be collected at Screening and Day 1 of every cycle through Cycle 6, followed by every 6 months thereafter, and at EOT.
- 24. From the time of informed consent signing through the first dose of IMP, SAEs resulting from a study-related procedure and assessed as related to that procedure, as well as all fatal AEs whether or not related to research procedures, must be recorded. All AEs will be recorded from all subjects from the date of first dose through 30 days following the last dose of ivosidenib and/or nivolumab or ipilimumab, whichever occurs later. Following the 30-day Safety Follow-up period, any SAEs that occur within 100 days after last dose of immunotherapy are to be reported, or until the subject initiates another anti-cancer therapy, whichever is earlier. Only SAEs that are considered as related to either IMP by the Investigator are to be reported after the respective Safety Follow-up periods. Fatal events, related or not to the research, occurring after ICF signature and before first IMP administration, must be reported on an AE form.
- 25. All concomitant medications/procedures within 21 days of the first dose of IMP through 30 days (+ 5 days) after the last dose of ivosidenib and/or immunotherapy and through 100 days after the last dose of immunotherapy (whichever is later) are to be reported on the eCRF.
- 26. Subjects will be contacted every 12 weeks (± 2 weeks) after the subject experiences documented disease progression or begins subsequent anti-cancer therapy for up to 2 years after the last subject has been enrolled, or until death, lost to follow-up, withdrawal of consent from overall study participation, or Sponsor ending study, whichever occurs first

Paragraph impacted 8.4 Definition of Serious Adverse Events

Amended text:

An SAE is any AE that, at any dose:

results in death,

is life-threatening⁽¹⁾,

requires insubject hospitalization or prolongation of existing hospitalization,

is medically significant⁽²⁾,

results in persistent or significant disability/incapacity⁽³⁾,

is a congenital anomaly/birth defect⁽⁴⁾.

All SAEs must be reported to the sponsor immediately, i.e., without delay and within 24 hours of awareness at the latest.

⁽¹⁾ Life-threatening in this context refers to an event in which the participant was at risk of death at the time of the event; it does not refer to an event which hypothetically might have caused death if it were more severe.

⁽²⁾ Any event that might not be immediately life-threatening or result in death or hospitalization, but might jeopardize the participant or might require intervention to prevent one of these outcomes (for example: oedema or allergic bronchospasm that required intensive treatment at home, blood dyscrasias, convulsions that do not result in hospitalization, or development of drug dependence or drug abuse). The Investigator should exercise his/her scientific and medical judgement to decide whether or not such an event requires expedited reporting to Sponsor.

⁽³⁾ Disability/incapacity in this context refers to any event that seriously disrupts the ability of the participant to lead a normal life, in other words leads to a persistent or permanent significant change, deterioration, injury or perturbation of the participant's body functions or structure, physical activity and/or quality of life.

⁽⁴⁾ Congenital anomaly or birth defect refers to the exposure to the IMP before conception (in men or women) or during pregnancy that resulted in an adverse outcome in the child.

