8.4. Definition of Serious Adverse Events

An SAE is any AE that, at any dose:

- results in death,
- is life-threatening⁽¹⁾,
- requires insubject hospitalization or prolongation of existing hospitalization,
- is medically significant⁽²⁾,
- results in persistent or significant disability/incapacity⁽³⁾,
- is a congenital anomaly/birth defect⁽⁴⁾.

⁽¹⁾ Life-threatening in this context refers to an event in which the participant was at risk of death at the time of the event; it does not refer to an event which hypothetically might have caused death if it were more severe.

⁽²⁾ Any event that might not be immediately life-threatening or result in death or hospitalization, but might jeopardize the participant or might require intervention to prevent one of these outcomes (for example: oedema or allergic bronchospasm that required intensive treatment at home, blood dyscrasias, convulsions that do not result in hospitalization, or development of drug dependence or drug abuse). The Investigator should exercise his/her scientific and medical judgement to decide whether or not such an event requires expedited reporting to Sponsor.

⁽³⁾ Disability/incapacity in this context refers to any event that seriously disrupts the ability of the participant to lead a normal life, in other words leads to a persistent or permanent significant change, deterioration, injury or perturbation of the participant's body functions or structure, physical activity and/or quality of life.

⁽⁴⁾ Congenital anomaly or birth defect refers to the exposure to the IMP before conception (in men or women) or during pregnancy that resulted in an adverse outcome in the child.

It is under Investigator's responsibility to evaluate the AE seriousness according to international guidance (see [ICH Topic E2A](#) and [EU DIRECTIVE 2001/20/EC of 4 April 2001](#) or further [regulation \(EU\) No 536/2014](#)). The Sponsor will review the AE seriousness. The seriousness may be upgraded (but never downgraded).

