8.10.2.5. Procedure for an Event Requiring an Immediate Notification

In case of an event requiring an immediate notification, the Investigator must:

- **Immediately** after being informed of this event, **fill in the participant's medical file** as well as the **Adverse Event form** of the eCRF (for SAEs and AESIs if applicable) according to the general instructions available in the eCRF, without waiting for the results of the clinical outcome or of additional investigations. When data will be submitted into the eCRF an email will be immediately and automatically sent to the Sponsor. However, for special situations requiring an immediate notification (as defined in Section 8.10.2.3) the completion of the Adverse Event form should not be performed systematically.
- If requested by the Sponsor (person designated in the contact details provided in the Investigator's study file), provide anonymized copies of the documents that provide additional useful information.
- Fulfil Investigator regulatory obligations to the Competent Authorities and/or to the IRB/IEC, in accordance with local regulations.
- In case of an SAE occurring in a first-in-human study, if the Investigator establishes or even suspects a relationship with the study protocol, they must immediately suspend the administration of IMP (and AxMP if applicable) in all participants. In this case, the written consent of the enrolled participants must be obtained again before the study is resumed.

Moreover, on request, the Investigator should provide the Sponsor with the documents required in Section 8.10.2.1.

If an AE that is initially non-serious worsens and becomes an SAE, this must be reported **immediately** on an “Adverse Event” form of the eCRF.

In case the eCRF is unavailable when the Investigator was informed of an AE to be reported immediately, the Investigator should:

- **Immediately** fill in a paper Adverse Event page:
 - For serious event, on a paper Adverse Event – Initial Information page.
 - For event initially non-serious, on a paper Adverse Event – Initial Information page, and the worsening leading to seriousness on a paper Adverse Event – Additional Information page.
- Immediately send the page(s) by email to the person(s) designated in the contact details provided in the Investigator's study file or outside working hours, the 24-hour phone number.
- As soon as the eCRF becomes available, the Investigator should enter these data in the Adverse Event form of the eCRF.

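### Footnote 2 of Protocol Section 8.4 makes expedited reporting of a medically significant SAE a matter of judgement, which contradicts the UK 24-hour rule for all SAEs and fits poorly with Section 8.10.2.5

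*Protocol*

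**What the plan says.** Protocol Section 8.4 lists six criteria, any one of which makes an adverse event serious. Appendix 13 (the UK modification) repeats the list. One criterion is that the event "is medically significant", and footnote 2 is attached to it. The footnote defines the category, starting with "Any event that might not be immediately life-threatening or result in death or hospitalization, but might jeopardize the participant". It gives examples such as bronchospasm treated intensively at home, blood dyscrasias and convulsions without hospitalization. Its last sentence in the UK text is: "The Investigator should exercise his/her scientific and medical judgement to decide whether or not such an event requires expedited reporting to Sponsor". The footnote in the main Section 8.4 ends in the same way; there too the investigator is "to decide whether or not such an event requires expedited reporting to Sponsor".

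The UK text adds a sentence after the six criteria: "All SAEs must be reported to the sponsor immediately, i.e., without delay and within 24 hours of awareness at the latest". The list of modifications at the head of Appendix 13 gives the purpose: "Clarification added to section 8.4 that all SAEs must be reported to the sponsor immediately and within 24 hours of awareness at the latest". The main Section 8.4 has no such sentence.

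Section 8.10.2.5, which applies at all sites, opens with "In case of an event requiring an immediate notification, the Investigator must". It then calls for immediate completion of the medical file and the adverse event form, the latter "for SAEs and AESIs if applicable".

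**The concern.** A footnote that defines one kind of SAE goes on to say that prompt reporting of that kind is discretionary. In the UK text this stands beside a sentence that covers every SAE, and it works against the stated purpose of the modification. An investigator who follows the footnote literally could class an event as serious and still judge that it need not go to the sponsor quickly.

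What is at stake is the time at which the sponsor learns of the event. Under Section 8.10.3 the sponsor reviews seriousness and causality, determines expectedness, reports suspected unexpected serious reactions to authorities and ethics committees, and informs investigators. None of this can start before notification. The combination is being tested for the first time, and Section 8.7 warns that immune-related events may appear several months after the last dose, well beyond the 42-day DLT window.

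**Working it through.** No arithmetic applies; the check is to set the passages side by side.

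| Place | What it says of a medically significant SAE |
|---|---|
| 8.4 criteria (main and UK) | It is an SAE |
| 8.4 footnote 2 (main and UK) | The investigator judges whether expedited reporting is needed |
| 8.4 added sentence (UK only) | Mandatory, within 24 hours of awareness, for all SAEs |
| 8.10.2.5 (all sites) | Immediate completion of the form for SAEs, once the event is one that requires immediate notification |
| 8.10.1 (all sites) | Reportable on an adverse event form; sets how long events remain reportable, not how fast they are sent |

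1. **Is the event already an SAE?** Yes. The footnote explains a criterion on the list, and meeting any criterion makes the event serious.

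2. **What does the judgement decide?** As written, whether expedited reporting is required. It does not say that the judgement decides seriousness. Section 8.6.1.1 pairs expedited reporting procedures with a 24-hour limit for QT prolongation, so the footnote appears to concern the same kind of prompt notification as the UK sentence.

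3. **UK text.** Steps 1 and 2 give an SAE whose prompt reporting is optional; the added sentence allows no exception. Both cannot be followed when the judgement is negative.

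4. **Main text.** The conflict is less direct. Section 8.10.2.5 treats SAEs as immediate, but its opening condition is an event that needs immediate notification. Footnote 2 can be read as deciding whether that condition is met, so the section does not clearly remove the discretion.

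5. **How wide is it?** One criterion of six. Footnotes 1, 3 and 4 only define terms, and death and hospitalization carry no footnote.

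6. **What is left unaffected?** The event must still be recorded and reported on an adverse event form. Only timing is in question.

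**The case against.** The strongest reply is that the documents already settle the matter in favour of prompt reporting. In the UK, a mandatory sentence with a stated purpose should override an inherited definitional footnote. At all sites, Section 8.10.2.5 calls for immediate entry for SAEs, with an automatic email to the sponsor. It requires immediate reporting when a non-serious event becomes serious, and its fallback for an unavailable eCRF includes serious events. None of these lines exempts medically significant events. Section 8.10.2.3 also glosses immediate notification as within 24 hours, for pregnancy and for intake by another person. This stands as a reason to expect prompt reporting in practice. It does not remove the sentence that says otherwise.

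A second reply is that the footnote was meant as a judgement on seriousness. Its definition is tentative enough to need one, and in the main text the footnotes are followed by a statement that the investigator evaluates seriousness. That is probably the intention, and the fix adopts it. It is not what the sentence says.

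Third, the effect on this trial is small. The SAP reports that enrolment stopped after 7 patients, that the Expansion phase did not open, and that a termination letter was issued on 21 August 2024. This stands, with one limit: Section 8.10.1 keeps related SAEs reportable whatever their time of onset.

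A reader might infer that, apart from DLTs (Section 4.1.4.4) and QT events (Section 8.6.1), medically significant SAEs have no 24-hour rule. The documents do not support that. Section 8.5.1 sets 24 hours for serious events associated with overdose or incorrect administration, Section 8.12.4 sets it for Grade 3 or 4 infusion reactions that meet SAE criteria, and the UK sentence covers all SAEs. What the main text lacks is a general hour count for SAEs.

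**Conclusion.** The point holds as a contradiction in current text: direct in the UK version of Section 8.4, and an unresolved tension with Section 8.10.2.5 at other sites. It affects one seriousness criterion of six and concerns the timing of notification only. No analysis set, endpoint or estimate changes.

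Two stronger readings should be resisted. One is that a class of SAEs will reach the sponsor late. The documents show only that late notification is possible; most of the surrounding text points the other way. The other is to size the problem from the cited nivolumab plus ipilimumab trial (Section 2.5), in which 6 of 39 subjects had Grade 3 or 4 immune-related events. That figure counts grade, not seriousness. It does not isolate events serious only through medical significance, and footnote 2 is not confined to immune-related events. No count of affected events can be derived.

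The conclusion assumes that sites follow the protocol wording. Figure (8.10.1) 1 is not shown and was not relied on. The eCRF instructions mentioned in Section 8.10.2.5 are not among the documents and might settle the matter for sites. The correction is worth making because a written rule on safety notification should not contradict itself.

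**What to change.** Reword the last sentence of footnote 2 in both the main Section 8.4 and Appendix 13. For example: *Scientific and medical judgement is used to decide whether such an event is medically significant and therefore serious; once classed as an SAE, it is notified to the Sponsor like any other SAE.* In the UK text, this should refer to the 24-hour sentence above it. In Section 8.10.2.5, state that every SAE is an event requiring immediate notification, so that the opening condition leaves no room for the discretion.

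Stating the UK 24-hour limit in the main Section 8.4 as well would give all sites one explicit deadline. This is optional harmonisation.

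The drafting cost is a sentence in each of three places, with perhaps a few more events sent promptly. The sponsor would need to decide whether the change is a substantial amendment; if so, Section 17.1.2 requires an ethics committee opinion and submission to the authorities. With enrolment closed, the benefit here is limited to remaining treatment and follow-up. The wording should also be checked before it is reused in another protocol.
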